2.2.2 Secondary endpoints

Groups A and B:

- progression-free survival at 6 months (PFS-6)
- median progression-free survival (PFS)
- median overall survival (OS)
- OS at 9 months (OS-9)
- for patients with measurable disease after debulking: best overall response distribution (BOR), objective response rate (PR+CR), complete response rate and duration of response (DOR)
- quality of life (QOL)

Group C:

- median progression-free survival (PFS)
- median overall survival (OS)
- OS at 9 months (OS-9), 1 year (OS-12)
- for non-surgical patients or patients with surgery for recurrence, but measurable disease thereafter: best overall response distribution (BOR), objective (PR+CR) rate, complete response rate and duration of response (DOR)
- success rate defined as rate of patients achieving either confirmed CR or PR (> 4 weeks) or free of progression at 6 months
- neurological progression-free survival (NPFS) based on the Neurologic Assessment in Neuro-Oncology (NANO): median NPFS and NPFS at 6 months (NPFS-6).
- clinical deterioration free survival (CDFS).
- safety profile (CTCAE)

pharmacokinetic profile of TG02: pre-dose, 30 minutes, 1 hour, 2 hours, 4 hours, 8 hours and 24 hours after the intake of TG02

In all groups:

- Correlation of molecular markers including MYC, MCL-1, CDK9 and CDK5 protein levels, and potentially others, with measures of clinical benefit.

3 Patient selection criteria

Patients must fulfill all of the following criteria to be eligible for registration in the study:

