7.2.2 Efficacy

To ensure a homogeneous radiological evaluation, all MRI images will be retrospectively centrally reviewed.

The following criteria will be used to determine the efficacy of study treatment.

Progression Free Survival (PFS): PFS is defined as the number of days from consent to the date of earliest disease progression based on Response Assessment in Neuro Oncology (RANO) criteria (as determined by the Investigator) or to the date of death, if disease progression does not occur. In group C, patients for whom neither death nor progression have been documented will be censored on the date of the last radiological assessment if they have no post anti-cancer therapy. If a patient has other post anti-cancer therapy prior to progression or death, the data will be censored at the date of last radiological assessment prior to or on the start date of post anti-cancer therapy. In group A and B, post anti-cancer therapy is not collected. The data will be censored at the date of the last radiological assessment. In all groups, if a patient with no post-baseline radiological assessment did not experience progression nor died, then the data will be censored at the date of enrollment.

PFS at 6 months (PFS-6) is the PFS rate at 6 months extracted from the PFS Kaplan Meier distribution based on RANO criteria (as determined by the Investigator)

Overall Survival (OS): OS is defined as the number of days from consent to the date of death due to any cause. If a patient has not died, the data will be censored at the last date documented to be alive.

OS at 9 months (OS-9) is the OS rate at 9 months extracted from the OS Kaplan Meier distribution.

Objective (ORR) and complete (CR) response rates are the proportions of patients with best overall response PR+CR or CR (see below) respectively.

Duration of objective (complete) response (DOR): DOR is determined as the number of days from the time point where the overall response PR or CR (CR) was first seen to the earliest date of detection of disease progression based on RANO criteria (as determined by the Investigator) or to the date of death, if disease progression does not occur. The same censoring rules defined above for PFS are applicable.

A success is defined as a patient achieving either confirmed CR or PR (> 4 week) or free of progression at 6 months.

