7.2.3 Definition of Response and progression

PFS6 is the primary endpoint for Group C. Additionally; several secondary endpoints are based on neuroimaging as assessed by MRI: the response rate, median progression-free survival, and the progression-free survival at defined time points. The sites should base their estimate of response according to the RANO criteria (Ref. 36) which would also be state of the art outside a clinical trial. The subsequent MRIs will be compared to the baseline MRI as defined in Section 7.2.5. In brief, the following definitions apply:

- **Complete Response (CR):** complete disappearance of all enhancing measurable and nonmeasurable disease sustained for at least 4 weeks; no new lesions; stable or improved nonenhancing (T2/FLAIR) lesions; patients must be off corticosteroids (or on physiologic replacement doses only); and stable or improved clinically. Note: Patients with nonmeasurable disease only cannot have a complete response; the best response possible is stable disease.
- **Partial Response (PR):** 50% decrease compared with baseline in the sum of products of perpendicular diameters of all measurable enhancing lesions sustained for at least 4 weeks; no progression of nonmeasurable disease; no new lesions; stable or improved nonenhancing (T2/FLAIR) lesions on same or lower dose of corticosteroids compared with baseline scan; the corticosteroid dose at the time of the scan evaluation should be no greater than the dose at time of baseline scan; and stable or improved clinically. Note: Patients with nonmeasurable disease only cannot have a partial response; the best response possible is stable disease.
- **Stable disease (SD):** does not qualify for complete response, partial response, or progression; stable nonenhancing (T2/FLAIR) lesions on same or lower dose of corticosteroids compared with baseline scan. In the event that the corticosteroid dose was increased for new symptoms and signs without confirmation of disease progression on neuroimaging, and subsequent follow-up imaging shows that this increase in corticosteroids was required because of disease progression, the last scan considered to show stable disease will be the scan obtained when the corticosteroid dose was equivalent to the baseline dose.

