8.2.2 Statistical methods

Group A and B

Primary endpoints are the determination of the Maximum Tolerated Dose (MTD) and the recommended phase II combination dose. All analyses will be performed in the safety population. Analyses will be descriptive only presented with tables and listings (i.e. no formal inference). Objective response rate will be reported with exact (binomial) 95% two-sided confidence interval. The PFS-6 and OS-9 and the medians will be extracted from their Kaplan-Meyer curves. The 95% two-sided confidence intervals will be computed based on the Greenwood's formula and based on the Reflected Method for the median. The best overall response will be presented in contingency table with numbers and percentages. The objective response (CR+PR) and complete response (CR) rates will be reported with exact (binomial) 95% two-sided confidence interval. Duration of objective response and complete response will be estimated using Kaplan-Meier methodology. Median duration of objective and complete response with corresponding 95% two-sided confidence interval provided by the Reflected Method will be displayed. Hematological and biochemistry parameters will be presented with clinical significance (CS vs NCS).

Safety and efficacy data in patients excluded from the safety population will be reported separately.

Group C

- Number of patients free of progression at 6 months (primary analysis)

In the efficacy population:

All patients will be observed during a minimum follow-up of 6 months. The number of patients free of progression and alive at 6 months will be computed and the above-mentioned decision rule applied. Patients lost to follow-up or who died before 6 months are considered as failures at the time of analysis. In case more than 45 eligible patients are recruited, the decision rule will be applied as such on the first 45 eligible patients. The proportion of patients free of progression at 6 months will be presented with 80% two-sided confidence intervals computed based on the Exact Binomial distribution.

- Progression free survival

In the efficacy population:

The primary endpoint, PFS rate at 6 months (PFS6) and the median PFS will be extracted from the Kaplan-Meyer PFS curve. For PFS6, 80% two-sided confidence intervals and 95% two-sided confidence intervals will be computed based on the Greenwood's formula. For the median the Reflected Method will provide 95% two-sided confidence intervals.

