These estimates will be presented both based on investigator and centrally reviewed progression data.

- Overall survival

In the efficacy population:

The OS rate at 9 months (OS-9), 1 year (OS-12) and the median will be extracted from the Kaplan-Meyer OS curve. For OS-9 and OS-12 95% two-sided confidence intervals will be computed based on Greenwood's formula. For the median the Reflected Method will provide 95% two-sided confidence intervals.

- Response and duration of response

In the efficacy population:

The best overall response will be presented in contingency table with numbers and percentages. The objective response (CR+PR) and complete response (CR) rates will be reported with exact (binomial) 95% two-sided confidence interval.

Duration of objective response and complete response will be estimated using Kaplan-Meier methodology. Median duration of objective and complete response with corresponding 95% two-sided confidence interval provided by the Reflected Method will be displayed.

These estimates will be presented both based on investigator and centrally reviewed response data.

- Success rate

In the efficacy population:

The success rate will be reported with exact (binomial) 95% two-sided confidence interval.

Success rate will be presented both based on investigator and centrally reviewed response data.

- Neurologic progression free survival

In the efficacy population:

The NPFS rate at 6 months (NPFS6) and the median NPFS will be extracted from the Kaplan-Meyer PFS curve. For NPFS6, 95% two-sided confidence intervals will be computed based on the Greenwood's formula. For the median the Reflected Method will provide 95% two-sided confidence intervals.

- Comparison of PFS by local investigator and by central review and comparison of NPFS and CDFS.

In the efficacy population:

The differences of times to event between these estimates will be tabulated.

- Safety and tolerability

In the safety population:

The safety and tolerability analyses will be presented at baseline and up to 30 days after the last administration of study drug. Baseline will include all information recorded up to the nearest date prior to or at randomization. Exceptionally in absence of this assessment, the first assessment performed after randomization but before start of protocol treatment can be considered as baseline.

Baseline laboratory and AE grades will not be accounted for in whole treatment safety analyses.

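### Section 8.2.2 does not carry over the measurable-disease restriction that 2.2.2 places on the response endpoints, so the denominator of the response rates is contradictory

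*Combined protocol and SAP*

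**What the plan says.** **Endpoint definition.** Section 2.2.2, repeated in the protocol summary, attaches the response endpoints to a subset. In Groups A and B they apply to patients whose disease is still measurable once debulking has been done. In Group C the entry reads "for non-surgical patients or patients with surgery for recurrence, but measurable disease thereafter: best overall response distribution (BOR), objective (PR+CR) rate", followed by the CR rate and duration of response.

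**Efficacy criteria.** Section 7.2.2 drops the subset: the "response rates are the proportions of patients with best overall response PR+CR or CR".

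**Analysis.** Section 8.2.1 defines three populations (intention-to-treat, efficacy, safety) and no response-evaluable set. For Groups A and B, 8.2.2 says "All analyses will be performed in the safety population". For Group C it puts the response analysis in the efficacy population, meaning all eligible patients who took at least one dose of TG02. In both places "The objective response (CR+PR) and complete response (CR) rates will be reported with exact (binomial) 95% two-sided confidence interval", with no mention of measurable disease.

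**Who can enter, and who can respond.** Section 3.1 requires debulking surgery in Groups A and B but no measurable residual tumor. In Group C it waives residual and measurable disease for patients operated on for recurrence, while non-operated patients must have a measurable lesion. Section 7.2.3 says "Patients with nonmeasurable disease only cannot have a complete response; the best response possible is stable disease", and likewise "Patients with nonmeasurable disease only cannot have a partial response; the best response possible is stable disease".

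**The concern.** The endpoint section and the analysis section give different denominators for the same rate, and neither refers to the other. Two statisticians could each follow the document and report different response rates from the same data.

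The difference runs in one direction. Patients without measurable disease can add to the denominator but, under 7.2.3, never to the numerator. Moving from the 2.2.2 subset to the whole population named in 8.2.2 can therefore only lower the ORR and CR rate, and it shifts the BOR table away from response categories. It also narrows the exact interval by counting patients in whom response is impossible. The result would be harder to compare across the three groups, because the route by which such patients enter differs between them.

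**Working it through.** **1. The plan's own figure.** The documents give no expected rate, threshold or precision for ORR. The only calculated figure is the Group C design on PFS-6 (8.1.1: 45 patients, success at 13 or more, P0 = 20%, P1 = 40%, α = 0.10, β = 0.05). Exact binomial results:

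- P(X ≥ 13 | n = 45, p = 0.20) = 0.0995, within 0.10.
- P(X ≥ 13 | n = 45, p = 0.40) = 0.9554, so β is within 0.05.
- One-sided 90% exact lower limit for 13/45 = 0.2002, above 0.20.
- 45 / (1 − 0.10) = 50, the stated total.

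The design reproduces. It counts patients alive and free of progression, not responders, so the denominator question does not touch it.

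**2. Can patients without measurable disease respond?** The notes in 7.2.3 cap patients with nonmeasurable disease only at stable disease. For a patient with no enhancing residual at all, PR needs a 50% decrease in measurable lesions and CR needs enhancing disease to disappear, so neither has a starting point. Section 7.2.5 foresees both situations: residual tumor under 10 x 10 mm, and gross total resection of the enhancing lesion.

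**3. Formula.** Let N be the population named in 8.2.2, f the share without measurable disease and x the number of responders.

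- 2.2.2 denominator: ORR = x / [N(1 − f)]
- Literal 8.2.2 denominator: ORR = x / N
- Literal rate = 2.2.2 rate × (1 − f)

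**4. Size.** Neither f nor the response rate is in the documents, so both are illustrative assumptions. For a 10% rate among measurable patients:

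- f = 0: 10% × 1.0 = 10% (no dilution)
- f = 20%: 10% × 0.8 = 8%
- f = 50%: 10% × 0.5 = 5%

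**5. Exact 95% intervals.** N is taken from 8.1.1 (45 in C; up to 24 in A and up to 12 in B). Assumed rates among measurable patients are about 20% in C and 30% in A and B, with counts rounded to whole patients.

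| Group | f | Measurable-disease denominator | Literal 8.2.2 denominator | Ratio of widths |
|---|---|---|---|---|
| C | 20% | 7/36 = 19.4% (8.2–36.0) | 7/45 = 15.6% (6.5–29.5) | 27.8/23.0 = 1.2 |
| C | 30% | 6/31 = 19.4% (7.5–37.5) | 6/45 = 13.3% (5.1–26.8) | 30.0/21.7 = 1.4 |
| C | 50% | 4/22 = 18.2% (5.2–40.3) | 4/45 = 8.9% (2.5–21.2) | 35.1/18.7 = 1.9 |
| A | 20% | 6/19 = 31.6% (12.6–56.6) | 6/24 = 25.0% (9.8–46.7) | 44.0/36.9 = 1.2 |
| A | 50% | 4/12 = 33.3% (9.9–65.1) | 4/24 = 16.7% (4.7–37.4) | 55.2/32.7 = 1.7 |
| B | 50% | 2/6 = 33.3% (4.3–77.7) | 2/12 = 16.7% (2.1–48.4) | 73.4/46.3 = 1.6 |

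**6. Duration of response.** Section 7.2.2 starts the clock at first PR or CR. Only responders contribute, so the denominator does not change it.

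**The case against.** The strongest reply is that 2.2.2 already fixes the denominator. Section 8.2.2 names a population for each endpoint and nowhere says that patients outside the endpoint definition are to be counted. The sensible combined reading is the 2.2.2 endpoint evaluated within the safety or efficacy population. That reading is available and may well be what the authors intend. It is not secured by the text: 8.2.2 states no subset, 8.2.1 defines none, and 7.2.2 gives a definition of the rate without the restriction.

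A second reply is that little depends on it. This largely stands. ORR is secondary, Groups A and B are declared descriptive with no formal inference, and no decision threshold uses response. Shifts of 2 to 5 percentage points on a 10% rate are small beside intervals such as 6.5–29.5%.

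Four stronger readings are tempting, and the documents do not support them:

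- *The reported rate would reflect surgery rather than drug activity.* It is the product of the rate among measurable patients and (1 − f), so it still depends on activity. In Groups A and B every patient has surgery; what varies is whether measurable tumor remains.
- *The dilution is known to be large.* No share is given. In Group C only operated patients without measurable residual disease contribute, and nothing indicates how many there would be.
- *Duration of response is biased too.* It is computed in responders only.
- *The trial's conclusions are at risk.* The MTD rests on DLTs and the Group C decision on PFS-6.

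**Conclusion.** The point holds as a conflict between stated rules for secondary endpoints. Followed literally, 7.2.2 and 8.2.2 yield BOR, ORR and CR rates that are not the endpoints defined in 2.2.2 and are lower by the factor (1 − f) whenever patients without measurable disease are enrolled. The direction follows from 3.1 and 7.2.3. The size rests wholly on the assumed f: zero if every patient has measurable disease, and a fall from 10% to 8% or 5% if 20% or 50% do not. The correction is worth making before analysis, but it changes neither the primary endpoints nor the design.

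**What to change.** In 8.2.1 or 8.2.2, state that BOR, ORR and CR rate are computed in patients of the stated population (safety for Groups A and B, efficacy for Group C) who have measurable disease on the baseline MRI, and that this denominator is reported with each rate. Align the ORR and CR definitions in 7.2.2. Because Group C response is shown by both investigator and central review, say which reading decides baseline measurability in each presentation. Duration of response needs no numerical change. The Group C success rate has no measurable-disease restriction in 2.2.2 and can stay as it is.

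The cost is a sentence or two of text. The baseline MRI is already required, so no new data or patients are needed. The price is precision: a smaller denominator widens the exact interval, by about 1.2 times at an assumed 20% share in Group C and by nearly twice at 50% (35.1 against 18.7 percentage points).

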Neurologic progression free survival (NPFS): NPFS is defined as the number of days from patient enrollment in trial until the date of first neurologic progression or the date of patient's death whichever occurs first, regardless of whether radiological progression has occurred or not. If a patient neither experienced neurologic progression nor died, then the data will be censored at the last date of post-baseline neurologic assessment. If a patient with no post-baseline neurologic assessment did not experience neurologic progression nor died, then the data will be censored at the date of enrollment.

Clinical deterioration free survival (CDFS): CDFS is defined as the number of days from patient enrollment in trial until the date of first clinical deterioration or the date of patient's death whichever occurs first, regardless of whether clinical deterioration has occurred or not. If a patient neither experienced clinical deterioration nor died, then the data will be censored at the last date of post-baseline Karnofsky performance score assessment. If a patient with no post-baseline Karnofsky performance score assessment did not experience clinical deterioration nor died, then the data will be censored at the date of enrollment.

See definitions below.

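### The Group C analysis text takes NPFS-6 and median NPFS from the PFS curve, contradicting the NPFS definition; the CDFS definition needs a matching correction

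*Combined protocol and SAP*

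**What the plan says.** Section 2.2.2 lists NPFS among the Group C secondary endpoints, with a median and a 6-month rate. It also lists CDFS, without naming a summary measure.

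Section 7.2.2 defines the endpoints separately. For PFS: "PFS is defined as the number of days from consent to the date of earliest disease progression", by RANO, or death. For NPFS, time runs from enrollment "until the date of first neurologic progression or the date of patient's death whichever occurs first, regardless of whether radiological progression has occurred or not". CDFS follows the same pattern with clinical deterioration as the event, but its closing clause reads "whichever occurs first, regardless of whether clinical deterioration has occurred or not".

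Section 8.2.2, under a heading for neurologic progression-free survival in the efficacy population, then states: "The NPFS rate at 6 months (NPFS6) and the median NPFS will be extracted from the Kaplan-Meyer PFS curve". It asks for a 95% Greenwood interval for the 6-month rate and a 95% Reflected Method interval for the median. CDFS appears in 8.2.2 only in the next item, which tabulates differences in event times, including those between NPFS and CDFS.

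**The concern.** The analysis instruction and the endpoint definition disagree. A programmer working from 8.2.2 alone would produce a table headed NPFS that contains the PFS results. This matters because section 2.1.2 makes the relation between NANO assessments and RANO outcome a secondary objective, and NPFS is the only NANO-based time-to-event endpoint analysed in 8.2.2.

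The CDFS clause is a second inconsistency of the same kind. A time to first clinical deterioration cannot be counted without regard to whether clinical deterioration has occurred. In addition, 8.2.2 does not say how CDFS itself is to be summarised, so that choice would be made after the data are known, in an open-label single-arm group.

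**Working it through.** No stated figure is in dispute, so the check is a comparison of the texts.

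**Step 1. Are PFS and NPFS the same variable in Group C?** From section 7.2.2:

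| | PFS | NPFS |
|---|---|---|
| Start | Consent | Enrollment |
| Event | RANO progression or death | Neurologic (NANO) progression or death |
| Radiological progression | Counts as an event | Does not count |
| Censoring, no event | Last radiological assessment | Last post-baseline neurologic assessment |
| New anticancer therapy before an event | Censored at the last scan on or before its start | No rule |

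The start dates should make little difference, because section 6.1.2 places Group C enrollment at the signing of consent. The event and the censoring rules do differ. So does follow-up: under sections 6.3.3 and 6.4.3, MRI continues every 3 months after treatment stops without progression, whereas NANO is scheduled only up to the end-of-treatment visit. The PFS curve is therefore not an NPFS curve.

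**Step 2. What does the surrounding text intend?**
- The NPFS sentence has the same form as the PFS sentence before it.
- Its intervals differ: PFS-6 gets 80% and 95% intervals, NPFS-6 gets 95% only.
- PFS is to be presented on both investigator and centrally reviewed data, so there are two PFS curves and no single one to read from.
- The tabulated comparison with CDFS needs patient-level NPFS times.
- Elsewhere 8.2.2 names the right source: OS from the OS curve, and the Group A and B endpoints from their own curves.

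These points indicate a drafting slip.

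**Step 3. What would the literal reading cost?** It would make NPFS-6 equal PFS-6, and the two medians equal, by construction. How far that would be from the truth cannot be found from the documents. As an illustration only, assume exponential times and an NPFS hazard r times the PFS hazard, with r from 0.5 to 1.2. With PFS-6 = p, the PFS hazard per month is h = −ln(p)/6, NPFS-6 = p^r, and median NPFS = ln 2/(h × r).

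| PFS-6 (p) | Median PFS | True NPFS-6, r = 1.2 | True NPFS-6, r = 0.5 | True median NPFS, r = 1.2 to 0.5 |
|---|---|---|---|---|
| 20% | 2.58 months | 0.20^1.2 = 14.5% | 0.20^0.5 = 44.7% | 2.15 to 5.17 months |
| 40% | 4.54 months | 0.40^1.2 = 33.3% | 0.40^0.5 = 63.2% | 3.78 to 9.08 months |

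In each row the literal instruction would report p and the PFS median. The values of p are the design's P0 and P1; the range of r is assumed.

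**Step 4. CDFS.** Section 7.2.2 gives it an event and a censoring date (last post-baseline Karnofsky assessment). Section 8.2.2 gives it no curve, median or interval, and section 8.2.3 adds intent-to-treat analyses for PFS and OS only. A table of differences from NPFS does not show how long patients stay free of deterioration, and the text gives no rule for a difference in which one of the two times is censored. In the NPFS definition, the position of the contradictory CDFS clause is filled by "regardless of whether radiological progression has occurred or not", which suggests what was meant.

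**Step 5. Primary analysis.** The rule of at least 13 successes in 45 has exact one-sided error 0.0995 at 20% and power 0.955 at 40%, within the stated 0.10 and 0.95. It uses neither NPFS nor CDFS.

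**The case against.** The strongest reply is that this is a one-letter slip which the documents resolve themselves. The heading, the full definition in 7.2.2, the separate interval specification and the comparison with CDFS all require a distinct NPFS variable, and a competent statistician would build one. That reply largely stands: the NPFS result is wrong only if 8.2.2 is followed to the letter.

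On CDFS, the reply is that section 2.2.2 promises neither a median nor a 6-month rate, so nothing promised has been dropped, and that CDFS is defined and used in the comparison. This also stands. What remains is a missing standalone summary, which is a matter of detail.

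On the CDFS clause, it can be said that the event is named in the same sentence, so the event date would probably be derived correctly anyway. That is likely, but the sentence still contradicts itself and should not remain in a definition.

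A reader might infer that two secondary endpoints will be wrong or missing, that Group C could not report time free of neurologic or clinical deterioration, or that identical results would be taken to show that NANO adds nothing to RANO. The documents do not support this. NANO and Karnofsky scores are collected on schedule, both times are defined in 7.2.2, and nothing prevents a proper Kaplan-Meier analysis of either.

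**Conclusion.** The inconsistency is real and should be corrected, but it is a drafting error with limited consequences. On the intended reading, the NPFS estimates are unaffected. On the literal reading, they would simply repeat PFS; the size of that error depends on hazards the documents do not give, and the ranges shown rest on assumed exponential times and assumed hazard ratios. The CDFS clause contradicts its own event and belongs in the same correction. The absence of a CDFS summary is a minor gap. Both endpoints are secondary and descriptive, and the Group C PFS-6 decision is unaffected.

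**What to change.** 1. In the NPFS paragraph of 8.2.2, replace PFS curve with NPFS curve and refer to the definition in 7.2.2.
2. In the CDFS definition in 7.2.2, correct the closing clause. The parallel NPFS sentence suggests that radiological progression was meant; the protocol authors should confirm this.
3. As a minor addition, give CDFS its own paragraph in 8.2.2: efficacy population, Kaplan-Meier curve, and median with a Reflected Method 95% interval. A 6-month rate with a Greenwood 95% interval is optional, since none is promised.

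The cost is a few words in two sections and one additional Kaplan-Meier table. No new data, visits or patients are needed.
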